3.3 Summary of preclinical immunogenicity studies

Although there are no animal models of HIV-1 infection that is highly predictive of what will be seen with vaccination in human clinical trials, immunogenicity studies are typically carried out in mice and monkeys, and challenge studies are often carried out in macaques with the SIV analogues of the candidate HIV-1 vaccines. As shown in the Table 3-1 below, preclinical immunogenicity studies were conducted in mice, rabbits and non-human primates with several of the VRC-HIV DNA and Ad5-vectored vaccines at the VRC and Beth Israel Deaconess Medical Center, Harvard Medical School (Boston, MA). The immunogenicity studies in mice and rabbits, as well as the non-human primate studies VRC-02-035 and VRC-03-060 were conducted using materials from the same exact bulk lots as those intended for clinical trials and formulated exactly as clinical trial material.

In summary, the studies shown below indicate that the previous generation of VRC DNA and Ad5 vaccines was able to induce partial protection from challenge in the SHIV model system, and that the improvements made with the current generation of both VRC candidate HIV vaccines (VRC-HIVDNA-016-00-VP and VRC-HIVADV-014-00-VP) can reasonably be

HVTN204_v1_PLoS Review.doc

May 24, 2005

expected to induce immune responses of greater magnitude and breadth than those from the earlier constructs. More detail on these studies can be found in the Investigator's Brochures.

Test System	Dose	Treatments per Animal	Treatment Period	Study Duration	Conclusions	References
Mouse	rAd: 1 x 10 ¹¹ PU	1	3 wks	4 wks	VRC-HIVADV014-00-VP immunization elicited humoral and cellular immune responses in mice.	Summary in VRC- HIVADV014-00-VP IB Section 5.3.1
Mouse	DNA: VRC- HIVDNA016-00-VP, 50µg	1	0 day	3 wks	Vaccination with the CMV/R plasmid encoding gag-pol-nef fusion protein (contained in VRC-HIVDNA016-00-VP vaccine product) elicits higher HIV-1specific cellular immune responses in mice than the unmodified 1012 plasmid encoding the same fusion protein (contained in VRC-HIVDNA009-00-VP vaccine product).	Summary in VRC- HIVDNA016-00-VP IB Section 4.2.1
Rabbit	DNA: VRC- HIVDNA009-00-VP, 4 mg rAd: 1 x 10 ¹¹ PU	6	106 days	119 days	Immunization VRC-HIVDNA009-00-VP DNA prime followed by VRC-HIVADV014-00-VP boost elicited humoral immune responses in rabbits.	Gene Logic (formerly TherImmune) Repeated Dose Toxicity Study #1195-114 and Summary in VRC- HIVADV014-00-VP IB Section 5.3.2
Rhesus macaques	DNA: (SIV) 10 mg rAd: 2 x 10 ¹² PU	3 DNA + 1 rAd	0, 4, 8 (DNA) + 26 wks (rAd)	64 wks	Immunization with SIVmac239 gag-pol-nef + (89.6P or HXB2 BaL nv DNA prime/rAd (no nef) boost confers partial protection against SHIV-89.6 challenge. Matched (89.6P) or mismatched (HXB2 BaL) Env immunogens conferred better immunity than vaccination without Env.	Study ASP-015 Letvin, et al. Virology (2004) 78:7490-7
Rhesus macaques	DNA: (SIV) 9 mg rAd: 1 x 10 ¹² PU	3 DNA + 1 rAd	0, 4, 8 wks (DNA) + 26 wks (rAd)	42 wks	Immunization with a four component multiclade vaccine resulted in broader responses without loss of immunogenicity to any component as compared with the vaccines consisting of plasmids and rAd expressing SIV Gag/Pol-(Nef) and HIV-1 Env from a single clade.	Study VRC-026A Summary in VRC- HIVADV014-00-VP IB Section 5.4.1
Cynomolgus macaques	DNA: 4-plasmid VRC- HIVDNA009-00-VP or 6-plasmid HIV-DNA016- 00-VP, 8 mg rAd:VRC-HIVADV014- 00-VP 1 x 10 ¹¹ PU	3 DNA 1 rAd	0, 4, 8 wks (DNA) + 38 wks (4- plasmid rAd boost) or 24 wks (6-plasmid rAd boost)	58 wks	Cynomolgus macaques receiving DNA prime/rAd boost immunization with the 6-plasmid DNA vaccine that expresses HIV-1 Gag, Pol, Nef and clade A, B and C Env (VRC-HIVDNA016-00- VP), and boosted with rAd expressing HIV-1 Gag/Pol and 3 Env, elicited cellular immune responses to all vaccine antigens. The 6- plasmid prime appeared t o be more immunogenic than the 4- plasmid DNA vaccine prime.	Study VRC-02-035 Summary in VRC- HIVDNA016-00-VP IB Section 2.3.2

Table 3-1 Summary of preclinical immunogenicity studies

4 Clinical studies

4.1 DNA plasmid vaccine trials

Human trials conducted with other plasmid DNA vaccines using similar clinical products have revealed no significant toxicity, autoimmunity, or other adverse reactions [14,17,27]. The status of completed and ongoing Phase I VRC, HVTN, and USMHRP studies with HIV-1 plasmid DNA vaccines developed by the VRC are summarized in Table 4-1 and briefly described below:

HIV DNA vaccine formulation	Study	Dose (mg)	# active doses planned (participants in active arm)	# active doses to date (participants in active arm)	Comment
VRC-HIVDNA009-00-VP	VRC 004	2.0 4.0 8.0	15 (5) 60 (20) 45 (15)	15 (5) 60 (20) 44 (15)	Vaccinations completed and study unblinded; also included 10 placebo participants (29 placebo injections)
4 plasmids (multiclade): clade B gag-pol-nef , clade A env , clade B env ,	HVTN 052	4.0	300 (120)	≥ 292 (120)	Of 540 blinded doses (300 active and 240 placebo) planned, 8 total were not given (still blinded).
clade C env .	RV 156	4.0	45 (15)	~30 (15)	Enrollment initiated in January 2005. Study also includes 15 placebo participants (45 planned placebo injections)
VRC-HIVDNA016-00-VP 6 plasmids (multiclade): clade B gag , clade B pol ,	VRC 007	4.0	45 (15)	44 (15)	Vaccinations completed; open label; no placebos.
clade B nef , clade A env , clade B env , clade C env .	VRC 008	4.0	120 (40)	0	Initiation May 2005

Table 4-1 Multiclade HIV DNA vaccine experience in uninfected participants as of May 2005

Summary: A dose range of 2.0 mg to 8.0 mg was evaluated for the 4-plasmid DNA vaccine. The majority of experience is with the 4.0 mg dose. This dose range was well tolerated.

Phase I studies (uninfected participants) include plans for 630 vaccine injections in 230 participants.

As of May 5, 2005, 190 uninfected participants have received one or more vaccine injections.

Note: Experience with a clade B single plasmid vaccine, with the 4-plasmid DNA vaccine in combination with an IL2/Ig adjuvant, and with the 4-plasmid DNA vaccine in HIV-infected participants is not shown. These studies together include more than 50 vaccinees to date.

4.1.1 Protocol VRC 001

The VRC completed a Phase I, randomized, controlled, double-blinded dose escalation study, VRC 001 (BB-IND 9782), to evaluate safety, tolerability, dose and immune response of an HIV plasmid DNA vaccine expressing a clade B Gag-Pol fusion protein (pGag (del fs)

PolΔPRΔRTΔIN/h; VRC-4302), which is similar in composition to VRC-HIVDNA009-00-VP and VRC-HIVDNA016-00-VP. Each of three groups of seven healthy, HIV-negative volunteers received a constant dose of the vaccine (5 people) or a phosphate buffered saline (PBS) control (2 people) by intramuscular inoculation. Once safety was established, successive groups received a higher dose. Study groups received three immunizations containing 0.5 mg (Group 1), 1.5 mg (Group 2), or 4.0 mg (Group 3) of the DNA vaccine or placebo. All 21 participants received all planned injections, which were well tolerated. All participants completed the study. There were no serious adverse events attributed to the study agent.

4.1.2 Protocol VRC 004

Protocol VRC-004 (03-I-0022) is a Phase I randomized, controlled, double-blinded dose escalation study to evaluate safety, tolerability, dose and immune response of a multiclade HIV plasmid DNA vaccine identified as VRC-HIVDNA009-00-VP. This study opened to accrual in November 2002 and was fully enrolled with 50 healthy HIV-negative participants in August 2003. Forty participants received vaccine injections and 10 participants received placebo injections. The three-injection schedule (administered at Weeks 0, 4 and 8), was completed in 5 of 5 participants randomized to 2 mg vaccine injections, 20 of 20 participants randomized to 4 mg vaccine injections, 14 of 15 participants randomized to 8 mg vaccine injections and 9 of 10 participants randomized to placebo injections. The unblinded final study results indicate that the vaccine injections were as well tolerated as the placebo injections.

greater responses in the 4 mg and 8 mg dose compared to the 2 mg dose, although not statistically significant. There was a statistically significant increase in the response after 3 injections compared to 2 injections at both the 4 mg and 8 mg dose levels, although there is no way to determine if this was due to the 3rd injection or simply a maturation of the response following the 2nd injection. Definitive responses are first detectable with the 4 mg and 8 mg dose at the 6-week time point (2 weeks after the second injection). When compared with the 8 mg dose, the 4 mg dose offers the combination of a good safety profile, greater ease of administration, and approximately equivalent cellular immunogenicity.

Fourteen of 35 vaccinees in the 4 mg and 8 mg groups had a positive ELISA at one or more points between Week 8 and Week 52 when tested by a commercial HIV antibody test. The optical density (O.D.) of the ELISA results usually decreased over time; six participants were ELISA positive by the commercial assay at Week 52.

Some VRC 004 participants may be offered the opportunity to enroll in a separate study (VRC 009) in which they could receive a single boost injection of VRC-HIVADV014-00-VP, a VRC recombinant adenoviral vector vaccine, at 1×10^{10} PU. That study will provide safety data of the adenoviral vector vaccine as a booster vaccine and will complement the immunogenicity data obtained in HVTN 057.

4.1.3 Protocol HVTN 044

Protocol HVTN 044 (BB-IND 10914) is a placebo-controlled Phase I study to evaluate the safety and immunogenicity of the 4 mg dose of the 4 plasmid multiclade VRC-HIVDNA009-00-VP vaccine administered in combination with escalating doses (0.1, 0.5, 1.5 and 4.0 mg) of a plasmid cytokine adjuvant VRC-ADJDNA004-IL2-VP (IL-2/Ig) in 70 HIV-negative participants. For this study, the multiclade DNA vaccine is being administered using the Biojector apparatus. The study opened for enrollment in December 2003, but is still accruing due to the multiple built-in safety pauses for the dose escalation of the adjuvant. As of March 2005, 54 out of 70 participants have been enrolled into this trial, 38 of which could have received the multiclade VRC-HIVDNA009-00-VP vaccine. All enrolled participants have received the first injection, 39 have received the 2nd injection, 31 have received the 3rd injection, and 17 have received all 4 injections.

4.2 Recombinant adenoviral vector vaccine trials

The status of completed and ongoing Phase I VRC and HVTN studies with the HIV-1 adenoviral vector vaccine developed by the VRC are summarized in the Table 4-2 and briefly described below:

Advaccing formulation	Study	Single	# active doses	# active	Commont
Au vacenie formulation	Study	dose (PU)	planned	doses to date	Comment
	VDC	10^{9}	10	10	Vaccinations completed.
	006	10^{10}	10	10	Study includes 6 placebo
	000	10^{11}	10	10	participants.
	VRC	10^{9}	20	0	Initiation May 2005
VRC-HIVADV014-00-VP	008	10^{10}	20	0	mitiation way 2003
4 adenoviral vectors with	VRC	1010	< 22	0	First enrolled in January
(multiplade);	009	≥ 52	0	2005	
(inuticiade):	VRC 10 ¹⁰	< 14	1	Eirst aprolled in May 2005	
clade B gug-poi	010	10	 	1	First enrolled in Way 2003
clade R env,	HVTN 10 ¹⁰		20	< 5	First enrolled in April
clade D env,	HVIN 054	$10 \\ 10^{11}$	20 20		2005. Study includes 8
clade C env	034	10			placebo participants.
	UUTN		60		Vaccinations completed.
	057	10^{10}		60	Study includes 10 placebo
					narticinants

Table 4-2 Multiclade HIV adenoviral vaccine, VRC-HIVADV014-00-VP, experience in uninfected participants as of May 2005

Summary: A dose range of 10^9 PU to 10^{11} PU has been evaluated in Phase I studies. The majority of experience is with the 10^{10} PU dose. Reactogenicity increases with higher doses, but the full dose range is well-tolerated. The experience as of May 2005 includes approximately 94 injections of the 10^{10} PU dose and 10 injections of the 10^{11} PU dose.

4.2.1 Protocol VRC 006

HVTN 054 is the second Phase I study of the rAd vaccine, VRC-HIVADV014, as a single agent in uninfected adult participants. This randomized, placebo-controlled, dose escalation study was submitted to BB-IND 11661 in December 2004 and opened to accrual in April 2005. It is designed to enroll two groups of 24 participants with low Ad5 neutralizing antibody titer (<1:12) that will be randomized to rAd or placebo in a 5:1 ratio. The first group of vaccinees will receive 10^{10} PU rAd and the second group will receive 10^{11} PU rAd.

4.3 Prime-boost trials

4.3.1 Protocol HVTN 057

HVTN 057 (BB-IND 11894) is the first Phase I study to administer the adenoviral vector vaccine, VRC-HIVADV014-00-VP, as a booster vaccination. In this blinded Phase I study a single boost at 10¹⁰ PU (or a placebo) is administered to participants who completed the injection regimen with VRC-HIVDNA009-00-VP or placebo in HVTN 052. The rAd boost is given at an interval of 6-9 months after the participant's first injection in HVTN 052. The first participant was enrolled on November 22, 2004, and on April 20, 2005 the last enrollment and study injection was completed.

As of May 13, 2005 the still blinded reactogenicity results indicated local pain and/or tenderness reported by 55 (78.6%) participants, with maximal severity moderate, reported for 3 (4.2%) participants. Erythema and/or induration no greater than 25 cm² was reported for 10 (14.3%) participants, of whom 7 (10.0%) reported the erythema and/or induration as <10 cm². Systemic reactogenicity did not exceed moderate: 18 (25.7%) reported mild symptoms and 6 (8.5%) reported moderate symptoms. The most commonly reported mild symptoms were malaise and/or fatigue in 20 (28.5%) participants, myalgia in 15 (21.4%) participants, and

headache in 10 (14.2%) participants. The most commonly reported moderate symptoms were headache in 7 (10.0%) participants, malaise and/or fatigue in 6 (8.5%) participants, and myalgia in 5 (7.5%) participants. Six (8.5%) participants reported grade 1 fever, none of which exceeded 38.5 $^{\circ}$ C.

4.3.2 Protocol VRC 009

VRC 009 is a Phase I study of rAd as a booster vaccine. It is an open label study designed to enroll subjects who completed three vaccinations with 4 mg or 8 mg of VRC-HIVDNA009-00-VP in VRC 004 (03-I-0022) to receive a 10¹⁰ PU rAd booster vaccination. The first enrollment into this study occurred January 28, 2005 and as of May 5, 2005 eight subjects were enrolled; four from the 4 mg group and four from the 8 mg group in VRC 004. The mean boost interval to date is 91 weeks [range 79-104 weeks] from first DNA prime vaccination. There have been no serious adverse events. All 8 subjects had mild pain at the injection site and 5 of 8 subjects had at least one mild or moderate symptom (malaise, myalgia, headache or chills). Seven of the 8 subjects have reached the first HIV ELISA testing time point and all have shown a vaccine-induced antibody by the commercial ELISA test method.

4.3.3 Protocol VRC 008

VRC 008 is a Phase I randomized study to examine safety and tolerability of and immune response to a prime-boost vaccination schedule. The schedule includes three doses of the 6-plasmid multiclade DNA-HIV vaccine, VRC-HIVDNA016-00-VP, at weeks 0, 4 and 8, followed by one dose of the multiclade HIV adenoviral vector vaccine, VRC-HIVADV014-00-VP, booster at week 24. Forty participants, half with high (>1:500) and half with low (\leq 1:500) adenovirus serotype 5 neutralizing antibody titers, will be randomized in a 1:1 ratio to receive the DNA vaccinations by either needle and syringe or by Biojector and also randomized in a 1:1 ratio to receive the booster vaccination with either 10¹⁰ PU or 10¹¹ PU of the adenoviral vector vaccine. The boost dose is blinded, but there are no placebo injections. This study opened to accrual in May 2005.

4.3.4 Protocol VRC 010

VRC 008 and VRC 010 (for VRC 007 rollover subjects) together (BB-IND 12326) will provide the Phase I safety and immunogenicity data for the prime-boost regimen that uses the 6-plasmid DNA vaccine, VRC-HIVDNA016-00-VP, for the priming vaccinations and VRC-HIVADV014-00-VP for the booster vaccination. The first rAd booster injection (10¹⁰ PU) of a subject primed with the 6-plasmid DNA vaccine occurred on May 4, 2005 when the first subject was enrolled into VRC 010.

5 Summary

5.1 Rationale for trial design

This Phase II study will investigate in a diverse population of study volunteers the safety and immunogenicity of a multiclade DNA plasmid prime followed by a multiclade, multivalent replication-incompetent recombinant adenoviral vector boost. Similar multi-clade, multivalent HIV inserts were used for these two vaccines to maximize the effect of priming and the breadth of the immune response, and to date studies show that the combination of vaccines similar to these are safe and well-tolerated. This protocol is on the critical path to qualify this vaccine combination for efficacy evaluation, and is intended to harmonize with two other studies currently in development, RV 172 and IAVI V001, which will be carried out in eastern Africa, respectively, by the US Military HIV Research Program (USMHRP) and the International AIDS Vaccine Initiative (IAVI).

HVTN 204, RV 172 and IAVI-V001 are designed to generate comparable safety and immunogenicity data from three distinct geographic regions, the Americas (HVTN 204), southern Africa (HVTN 204) and eastern Africa (RV172 and IAVI V001). As the Ad-5 seroprevalence in these regions is not yet precisely understood, the regional approach is being pursued to garner the safety and immunogenicity data that would be required to move the vaccination regimen forward in advanced phase clinical trials in one or more of the regions independently. In each region, 3 doses of 4 mg of the VRC DNA-HIV vaccine (VRC-HIVDNA016-00-VP) followed by a single 1×10^{10} PU dose of VRC Ad5-HIV vaccine (VRC-HIVADV014-00-VP) will be given to approximately 120 participants in identical vaccination schedules. In each region, an equivalent number (N \approx 120) of control vaccine recipients will be enrolled as well. In an attempt to assure that the variety of HIV transmission modes are represented among participants in HVTN 204, our goal is that at least 40% of participants will be male, in whom the predominant mode of transmission is assumed to be MSM contact in the Americas and heterosexual contact in southern Africa, and at least 40% of participants will be female, in whom the predominant mode of transmission is assumed to be heterosexual contact in both regions. Gender equity will also be the goal of the eastern Africa studies (RV 172 and IAVI V001).

HVTN 204 is powered to detect fairly small differences in safety and immunogenicity between the vaccine and placebo arms, and the three studies HVTN 204, RV 172, and IAVI V001 assessed together have excellent power to detect fairly small differences in safety and immunogenicity between the vaccine and placebo arms (see Section 9.4.3 for the minimum detectable effect sizes with high power). Taken together these studies should provide sufficient data to qualify the vaccine regimen for expanded studies of vaccine efficacy in these regions.

As pointed out earlier in this document, the relatively high prevalence of adenovirus type 5 immunity worldwide could attenuate the immune response to this adenoviral vector vaccine, and thus limit its usefulness as a global vaccine for adults. The current protocol is designed to evaluate the relationship between preexisting titers of neutralizing antibody to adenovirus 5 and immunogenicity of the combination vaccine regimen. In each region, the populations' existing background Ad5 seropositivity is being elucidated, and although in HVTN 204, RV 172, and IAVI V001 study participants will be enrolled without regard to preexisting Ad5 immunity (i.e., no Ad5 neutralizing antibody titer prescreening and stratification), the preexisting Ad5 neutralizing antibody titers will be determined and considered in the secondary analysis of the safety and immunogenicity data. Specifically, assessment of safety

and vaccine take rate among subsets of participants with lower levels of Ad5 neutralizing antibody titer will be performed. In addition, data across regions will be pooled to estimate the overall probability of vaccine take as a function of preexisting Ad5 neutralizing antibody titer. Results from these secondary analyses of trial data will also help in determining the design and projected sample size of future efficacy trials.

HVTN 204 will be initiated after a review of all available safety data from the several ongoing clinical trials evaluating the same or similar VRC candidate HIV vaccines. Specifically, this includes protocols evaluating 3 doses of 4 mg of DNA vaccines alone (VRC 001, VRC 004, VRC 007, and HVTN 052), 1 dose of 1 x 10^{10} PU of the adenoviral vector alone (VRC 006) and the combination of DNA prime and adenoviral vector boost (HVTN 057 and VRC 009).

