An analysis of reports to WHO between 1967 and 1976 found no difference between Northern and Southern Hemispheres in the relative incidence of Ad5 among reported adenovirus infections [74]. However, recent studies in sub-Saharan Africa have found the seroprevalence of neutralizing antibodies to Ad5 to be approximately 80-90% [71,75]. Merck, WRAIR, the HVTN and the VRC have recently collected, or are in the process of collecting seroprevalence data on neutralizing titers to Ad5 in many countries that have a high incidence of HIV infection (Table 1-1 and Table 1-2). Preliminary studies suggest that the titer of 1:200 in the Merck assay is roughly equivalent to the titer of 1:500 in the VRC assay. The significant prevalence of Ad5 immunity in these countries necessitates clinical investigation of the effect of prior immunity on the immunogenicity of type 5 adenoviral vector vaccines, and the development of strategies to overcome this effect, before large-scale clinical trials of such HIV vaccines are undertaken.

	<18	18-200	>200
	(%)	(%)	(%)
Brazil (n=183)	8.2	29.5	62.3
Botswana (n=63)	8.8	26.5	64.7
Cameroon (n=225)	8.9	28.9	62.2
Malawi (n=49)	12.2	32.7	55.1
South Africa (n=182)	10.4	21.4	68.2
Thailand (n=1006)	6.0	13.7	80.3
US (n=779)	38.8	25.4	35.8

Table 1-1 Ad5 neutralizing antibody titers tested by Merck & Co., Inc. [76]

Table 1-2 Ad5 neutralizing antibody titers tested by the VRC

	<12 (%)	12-500 (%)	>500 (%)
India (n=96)	19.8	29.2	51.0
Tanzania (n=53)	5.7	43.4	50.9
Uganda (n=110)	19.1	30.9	50.0
US (n=85)	50.6	10.6	38.8

1.2.4

Rationale for prime-boost vaccine strategies

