Regression methods will be used to model immunogenicity as a function of vaccine regimen and preexisting Ad5 neutralizing antibody titer. Moulton and Halsey's mixed gamma model will be considered.

Some immunologic assays have underlying continuous or count-type readout that is often dichotomized into responder/nonresponder categories. For these assays, graphical and tabular

summaries of the underlying distributions will be made. These summaries may be performed on transformed data (e.g., log transformation) to better satisfy assumptions of symmetry and homoscedasticity. If group comparisons in these underlying distributions reveal that differences are best summarized as a shift in the location of the distribution, then results will be presented in the form of group means (or medians) with associated confidence intervals and statistical tests for differences between groups as described above. If group comparisons in these underlying distributions reveal that differences are best summarized by a mixture model (i.e., responder and nonresponder subgroups are clearly identifiable) then results will be presented in the form of response rates with associated confidence intervals and statistical tests as described above.

Missing data

If the probability of missing immunogenicity measurements depends on either covariates or on the immunogenicity outcomes of participants, then the methods described above may give biased inferences and point estimates. If a substantial amount of immunogenicity data is missing (at least 1 value missing from more than 20% of participants), then secondary analyses of the immunogenicity endpoints will be conducted using methods that relax the missing completely at random assumption to a missing at random assumption. For a univariate binary and quantitative outcome, respectively, a generalized linear model with a binomial or normal error distribution will be used for estimation and testing. For assessing repeated immunogenicity measurements, linear mixed effects models will be used. The models will be fit using maximum likelihood methods, and will include as covariates all available baseline predictors of the missing outcomes. The longitudinal models will also include all observed immunogenicity data.

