9.6 Randomization of treatment assignments

The randomization sequence will be obtained by computer-generated random numbers and provided to each HVTU by the SDMC using the procedures described in the HVTN MOP. At each institution, the pharmacist with primary responsibility for drug dispensing is charged with maintaining security of the randomization list. The randomization will be stratified by geographic region and done in blocks to ensure balance across groups. Following an interim assessment of the distribution of pre-existing Ad5 antibody titers among participants enrolled in the trial, future enrollment may be redirected to certain sites in order to ensure that an approximate balance of low and high titer participants are enrolled. An approximate balance is defined as between 40% and 60% of participants with prior Ad5 titers >1:500. The interim assessment will also be used to verify that there is an adequate representation of men and women in the trial (e.g., the proportion of either cohort is at least 0.40).

STUDY OPERATIONS

10 Protocol conduct

The protocol will be conducted according to standard HVTN policies and procedures specified in the HVTN MOP (Study Operations), including procedures for the following:

Protocol registration, activation and implementation

- Informed consent, screening, enrollment
- Clinical and safety assessments
- Safety monitoring and reporting
- Data collection and documentation
- Study follow-up and close-out
- Unblinding of staff and participants
- Quality control
- Protocol monitoring and compliance
- Advocacy and assistance through local and governmental activities to participants regarding social harms associated with the vaccine trial
- Risk reduction counseling
- Outside testing and belief questionnaire

Any policies or procedures that vary from HVTN standards or require additional instructions will be described in the *HVTN 204 Study Specific Procedures* (e.g., instructions for randomization specific to this study).

11 Informed consent

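### The pooled Ad5 titer-response analysis names no region adjustment, so part of any regional difference in vaccine take can appear as an Ad5 effect

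*Protocol*

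**What the plan says.** Section 6.2 makes the relation between prior Ad5 antibody and immunogenicity a secondary objective. Three places in the Protocol describe how regions and titer enter.

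- Section 5.1: "data across regions will be pooled to estimate the overall probability of vaccine take as a function of preexisting Ad5 neutralizing antibody titer". The same paragraph says that these secondary analyses will help set the design and size of later efficacy trials.
- Section 9.5.4: "Regression methods will be used to model immunogenicity as a function of vaccine regimen and preexisting Ad5 neutralizing antibody titer". A mixed gamma model is to be considered. Region is not mentioned.
- Section 9.6: "The randomization will be stratified by geographic region and done in blocks to ensure balance across groups". After an interim look at titers, "future enrollment may be redirected to certain sites in order to ensure that an approximate balance of low and high titer participants are enrolled". The target is trial-wide: "An approximate balance is defined as between 40% and 60% of participants with prior Ad5 titers >1:500".

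The Protocol's own titer data are in Table 1-1 (section 1.2.3), with columns for titers below 18, 18 to 200 and above 200. Two rows are "US (n=779) 38.8 25.4 35.8" and "South Africa (n=182) 10.4 21.4 68.2". Botswana has 64.7% and Brazil 62.3% above 200. The text links that cut to the trial's own assay: "the titer of 1:200 in the Merck assay is roughly equivalent to the titer of 1:500 in the VRC assay".

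**The concern.** Stratified randomisation balances vaccine and placebo within region. It does nothing for a comparison of high-titer with low-titer vaccinees, because nobody is randomised to a titer. If one region contributes more of the high-titer vaccinees, and take differs between regions for any other reason (specimen handling, HLA or demographics, for example), the pooled titer curve absorbs part of that difference.

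The error can go either way. Lower take in the higher-titer region mimics or exaggerates attenuation by prior Ad5 immunity. Higher take there hides attenuation. Section 5.1 wants data that could move the regimen forward in one or more regions independently, and that requires regional and Ad5 effects to be told apart.

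**Working it through.** The plan gives no figure for this bias, so there is none to reproduce. The check asks how much of a regional difference reaches the titer contrast when titer has no effect within either region.

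**Inputs from the Protocol**
- 120 vaccinees per region (section 9.4). With the 10% loss used in section 9.4.2, 120 × 0.9 = 108 per region.
- High-titer share in southern Africa: hS = 0.682 (South Africa, Table 1-1).
- High-titer share in the Americas: hA = 0.358 if all US, 0.623 if all Brazil-like, and (0.358 + 0.623)/2 = 0.4905 if half and half.

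**Assumptions**
- The Americas country mix. The Protocol describes this region as the US, South America and the Caribbean in the Foreword but as US/Caribbean in section 9.4, and neither titer table has a Caribbean row.
- Take of 70% in the Americas and 50% in southern Africa. The Protocol gives no regional take rates.

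**Share that leaks.** With equal regions, the Americas make up hA/(hA + hS) of the high-titer group and (1 − hA)/(2 − hA − hS) of the low-titer group. The leak is the second minus the first. The spurious low-minus-high gap is the leak times the regional difference.

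| Americas mix | Low-titer group | High-titer group | Leak | Gap for 20 points |
|---|---|---|---|---|
| All US | 0.642/0.960 = 0.669 | 0.358/1.040 = 0.344 | 0.325 | 6.5 points |
| Half US, half Brazil-like | 0.5095/0.8275 = 0.616 | 0.4905/1.1725 = 0.418 | 0.197 | 3.9 points |
| All Brazil-like | 0.377/0.695 = 0.542 | 0.623/1.305 = 0.477 | 0.065 | 1.3 points |

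Using the mean of Botswana and South Africa, (64.7 + 68.2)/2 = 66.45%, the leaks are 0.31, 0.18 and 0.05.

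**False-positive rates.** Simulated trials, 108 vaccinees per region, 20-point regional difference, no Ad5 effect within region, two-sided 0.05:

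| Americas mix | Pooled chi-square | Mantel-Haenszel by region |
|---|---|---|
| All US | about 0.16 | about 0.05 |
| Half US, half Brazil-like | about 0.09 | about 0.05 |
| All Brazil-like | about 0.05 | about 0.05 |

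With an all-US mix, regional differences of 10 and 30 points give about 0.08 and 0.30. Fisher's exact test is somewhat lower: 0.066, 0.140 and 0.272 for 10, 20 and 30 points with all US, and 0.075 for 20 points with the half-and-half mix.

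**Does the balance rule help?** The trial-wide high-titer share is (35.8 + 68.2)/2 = 52.0% for all US, (49.05 + 68.2)/2 = 58.6% for the half mix and (62.3 + 68.2)/2 = 65.25% for all Brazil-like. The first two, where the leak is largest, satisfy 40% to 60%. The third, where it is small, does not and could trigger redirection. Regional totals are fixed, so lowering the high-titer share means using lower-titer sites within a region. Among the trial's named countries in Table 1-1, the low-titer one is the US.

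**Lower cut.** Titers below 18 are 38.8% in the US and 10.4% in South Africa. The leak is 0.388/0.492 − 0.612/1.508 = 0.789 − 0.406 = 0.383, or 7.7 points for a 20-point difference.

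**Adding eastern Africa.** With a third region of 108 vaccinees, 50% high titer (Uganda, Table 1-2) and an assumed 60% take, the all-US gap is (0.642 × 0.7 + 0.318 × 0.5 + 0.5 × 0.6)/1.46 − (0.358 × 0.7 + 0.682 × 0.5 + 0.5 × 0.6)/1.54 = 0.622 − 0.579 = 4.3 points. The pooled false-positive rate is about 0.12.

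**The case against.** The strongest reply is that the Protocol never excludes region. The sentence in section 9.5.4 is general, pooling can simply mean using everyone's data, and section 9.5.6 defers to analysis plans for this trial and for the three-study data, neither of which is shown. A reader might infer that region has been ruled out of the model. The text does not support that: region is unnamed, not excluded. What stands is that the Protocol commits to pooling, names two terms, and omits the one that its own table shows to be related to titer.

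A reader might also infer that any regional difference will be read wholesale as an Ad5 effect. It will not. Titer varies widely within each region, so only part leaks, and very little does if the Americas participants resemble Brazil. The marked tie between titer and region holds for the US, not for Brazil.

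A third tempting reading is that the threshold tests in section 9.4.2 are shown to be biased. They appear in a power calculation restricted to vaccinees above 1:500, and the documents do not show how titers above that cut are distributed by region. No size can be given for those tests.

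It is also fair to say that the analysis is secondary, that the regional differences in take are assumed, and that the region-specific estimates foreseen in section 9.4.3 would make a regional difference visible. Seeing such a difference would not, however, remove it from the pooled titer curve.

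**Conclusion.** The point holds in limited form. Followed as written, the pooled titer-response analysis is open to confounding by region, and the trial-wide titer balance rule does not guard against it. At the high-titer cut the leak runs from about 7% to about 33% of the regional difference in take (5% to 31% with the southern Africa average), and reaches 38% at the lowest-titer cut for the US against South Africa. Whether it matters depends on two things that the Protocol does not settle: the country mix in the Americas and the size of any regional difference in take. With a mostly US enrolment and a difference of 20 points or more, the false-positive rate is materially above 0.05. With a 10-point difference or a Brazil-like enrolment the excess is small or absent. Because the result is meant to inform efficacy-trial design and the remedy is nearly free, the change should be made.

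**What to change.** In section 9.5.4:
- include region, already the randomisation stratum, as a factor in every Ad5-response model, and use region or study in the combined three-study analysis;
- stratify high-against-low titer comparisons, and any threshold tests that are carried out, by region (Mantel-Haenszel or permutation within region);
- show titer-response curves within each region, with a check of the titer-by-region interaction;
- present the pooled curve in section 5.1 as one standardised over region.

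No new data are needed. Intervals for the titer effect become slightly wider because only within-region variation in titer is used.
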